12. OTHER STUDY PROCEDURES

12.1.1 Early Termination

Early termination visit

Participants may voluntarily withdraw from the study for any reason at any time. Field site investigators may withdraw a participant before their scheduled termination visit to protect their safety. Participants may be withdrawn if the study sponsors, government or regulatory authorities, IRBs/ERCs terminate the study prior to its planned end date. Site investigators are required to consult with the principal investigators prior to termination of any study participant. Study staff will record the reasons for all withdrawals in participants' study records. There are no pharmaceutical, surgical or ongoing biomedical interventions; early termination will primarily be behavioral in nature.

Voluntary Withdrawal

If a participant voluntarily withdraws from the study, an exit questionnaire/debrief will be administered to determine reasons for withdrawal and risk behavior assessment as well as VL tests if HIV positive (as would normally be done at end of 12-month cohort).

12.1.2 Pregnancy Visit

Participants who become pregnant will be allowed to continue in the study. **Our study does not include any pharmacological or surgical intervention.**

12.1.3 Unscheduled Visits

Unscheduled visits will occur by sending an invitation SMS text to the participant, calling them, or locating them using their participant locator information (also known as locator tracking form), details can be found in the informed consent procedures section 11.2. Participant initiated unscheduled visits occur when a participant initiates an unscheduled visit by, texting, calling, or stopping by in person.

13. STATISTICAL CONSIDERATIONS

13.1 Overview and Study Objectives

We will rigorously compare two 'seek' recruitment strategies, three 'test' strategies, and two enhancements to an adaptive (SMART trial design) 'linkage to care intervention, among young at-risk women who are 15-24 years old. Additionally, we will evaluate a scalable primary prevention messaging intervention to support identified HIV-negative young women in reducing HIV risk and adhering to recommended HIV re-testing recommendations. This study design will allow us to follow participants along both the prevention and care continua.

Primary Objectives:

1. To determine the preferred recruitment venue and testing modality that targets and finds the highest number of HIV infected and at risk female youth aged 15-24 years in Homa Bay County, Nyanza region, western Kenya. This will be determined by examining the uptake and yield of previously undiagnosed HIV infection of the two 'seek' strategies (community or home-based) and the three 'test' strategies (self-testing, HTS in a home/mobile setting, or facility-based HTS) among female youth;
2. To conduct an economic evaluation, using cost effectiveness analyses to determine the relative utility of each seek, test, link, and prevention intervention.

Secondary Objectives:

1. To pilot and evaluate an adaptive intervention to link newly diagnosed HIV-positive female youth to treatment and care services;
2. To identify barriers and facilitators to seeking HIV care services after receiving a positive diagnosis;
3. To identify barriers and facilitators to seeking HIV prevention services for high risk female youth after receiving a negative HIV test result;
4. To deliver an HIV prevention intervention to a randomly selected subset of high risk negative female youth, and to re-test them at 12 months.

13.2 Description of the Analyses

See Table 1: Evaluation Plan for Data Management and Analysis.

Baseline Data

1. Basic demographic information
2. Sexual risk behaviors
3. HIV risk behaviors
4. Attitudes/knowledge about HIV transmission and prevalence
5. Knowledge and acceptability of specific HIV prevention interventions

6. Knowledge and acceptability of family planning methods

The primary endpoint for comparisons of recruitment and testing strategies is newly diagnosed HIV infection. The key outcomes we detail below are broken out by study aims and based on the HIV prevention and treatment continua, which organizes our outcomes of interest by recruitment strategies, testing, linkage, retention and primary prevention.

Primary Endpoints

Primary outcomes of interest for Aim 1 is based on the HIV prevention and treatment continua as outlined below:

- Recruitment/Seek: Ability to identify and recruit female youths that are high risk for HIV infection using two seek strategies (home-based vs. community-based)
 - The proportion of youth in the community who accept study screening (estimated from total youth approached as the denominator);
 - The proportion of youth who accept study enrollment (estimated from youth screened and eligible as the denominator).
- Testing:
 - Testing uptake by different testing modalities;
 - Completion of confirmatory testing;
 - Proportion that are positive;
 - Among those who are positive, completion of baseline collection of CD4 and viral load tests.

Outcomes of interest for the Aim 3 economic evaluation include:

- Compute the cost per HIV-infected female youth identified under each 'seek' strategy (home-based vs. community based);
- Compute the cost per HIV-infected female youth identified under each 'test' strategy (self-testing, staff delivered HTS testing, standard facility-based HTS);
- Calculate the incremental cost-effectiveness ratio of the adaptive linkage to care intervention among HIV positive female youth;
- Compute the cost of the SMS prevention intervention among HIV negative female youth.

Secondary Endpoints

- Linkage to Care:
 - Percent of females who tested positive that attended a first HIV care appointment at an HIV Comprehensive Care Center (CCC)
 - Time to link to care after positive confirmatory test result
- Retention in Care:
 - Completion of viral load testing at 12 months;
 - Reported appointment attendance via SMS and verification by study staff at 3, 6, 9, and 12 months.
- Primary Prevention (N≈185):
 - Proportion reporting HIV risk behaviors, and condom use, at 6 and 12 months;
 - Proportion who re-tested at 12 months.
 - Proportion with a positive HIV test result for a sub-set of negatives at 12 months.

Statistical Analyses

Recruitment Strategy and Testing Modality: We will determine which HIV testing approaches are most preferred among all female youth and among higher risk female youth. We also will determine which recruitment and HIV testing approaches yield the highest rates of newly diagnosed HIV infection. Multinomial logistic regression (Hosmer & Lemeshow, 2004; Hosmer, Lemeshow, & Sturdivant, 2000) will be used to understand which testing approaches are most preferred/used by female youth. Preference for HIV testing at a health facility will be the reference category for the dependent variable. A model with only an intercept will be used to estimate the proportion of girls preferring each testing approach, and to test for pairwise differences in preferences (e.g., does a higher proportion of girls prefer staff-aided rather than self-testing?). In addition to overall preferences, we will consider age, risk behaviors, and HIV testing history as predictors of preferences by adding participant characteristics to the multinomial logistic regression analysis. Type of testing selected by participants, including refusal to test, will be regressed on predictors to estimate how characteristics of female youth impact HIV testing preferences. Model coefficients will describe the change in odds of preferring other types of testing relative to the reference category (facility-based testing).

Logistic regression analysis will be used to determine which recruitment and HIV testing approaches yield the highest proportion of newly diagnosed HIV infection. HIV testing result (negative vs. positive) will be regressed on variables indicating recruitment strategy (home vs. community) and type of HIV testing (self, staff-aided, facility-based). With facility-based testing following community-based recruitment as a reference category, we will estimate how home-based recruitment and other testing approaches change the odds of a positive test result. The interaction between recruitment strategy and HIV testing approach will be tested to determine whether the yield of each testing approach is conditional on recruitment strategy. If a significant interaction effect is found, simple main effects of testing approach within each recruitment strategy and simple main effects of recruitment strategy within each testing approach will be estimated. In addition to comparing yield by recruitment strategies and testing approaches, we will consider interaction effects with youth characteristics, such as age, risk behaviors, and HIV testing history, and type of testing. Similar logistic regression analyses will examine differences in the odds of completing all confirmatory testing by recruitment strategy and approach to testing.

Home-based and community-based recruitment strategies will also be compared to determine which strategy is more effective in reaching higher risk female youth. Rates of acceptance of screening among potential participants offered screening and rates of enrollment among eligible participants will be compared by recruitment strategy using logistic regression. Risk will be characterized by number and serostatus of sex partners, concurrency, condom use, and patterns of HIV testing by the participant and any sex partners.

A random selection of N≈185 girls with HIV negative tests will be followed-up. We will assess risk behaviors, condom use, additional HIV testing, linkage to prevention and any new HIV diagnoses over the year since study enrollment. Re-testing, prevention service use, and new HIV will be examined in relation to recruitment strategy, testing approach at enrollment, and participant risk behavior and other characteristics.

Adaptive Intervention Pilot: Descriptive statistics and survival plots will be used to characterize occurrence and timing of linkage among girls responding to the initial SMS message and girls in each augmented treatment condition. Survival analysis (Singer & Willett, 2003; Therneau & Grambsch, 2000) will determine which approach to augmenting linkage – continued SMS or economic incentives – is more effective in linking female youth newly diagnosed with HIV to care sooner. Using the Cox Proportional Hazards Model, difference in the likelihood and timing of linkage between treatment conditions will be quantified with an interval estimate of the hazard ratio. Median time to linkage also will be estimated and compared across treatment conditions.

Cost Effective Analysis

In order to determine costs, we will conduct a micro-costing of the cost per HIV-infected person identified under each ‘seek’ and ‘test’ strategy. This will be followed by an incremental cost-effectiveness analysis of the linkage to care interventions among HIV-infected, and a cost analysis of the SMS intervention among HIV-uninfected, women. These costs will include all costs required to deliver each intervention (home visits, staff time, supplies, and monitoring). Data will primarily utilize a micro-costing methodology that uses project expenditure and management records, employing structured costing spreadsheets that record each resource, category (e.g., personnel, supplies), quantity (e.g., hours), and unit costs. The cost data for the self-test group will include costs of obtaining a confirmatory test for those with positive self-testing results. The cost data will be stratified by HIV testing venue (home based, community based (mobile), or referral facility). With these cost data, we will calculate and compare the cost per HIV-infected person identified in each HTC strategy. We will also evaluate the costs of the linkage interventions per individual successfully linked to care. The results of the economic evaluation will allow us to identify the most efficient, affordable way to seek high risk young women and test them. For the linkage interventions, we will utilize the cost data as well as the effectiveness results to compute the ICER for the novel linkage intervention that is used. The ICER will reveal whether the costs of achieving the incremental gains from additional linkage intervention(s) suggest whether it is cost-effective or not. These results will provide novel data on the cost-effectiveness of linkage to care interventions for high-risk females in sub-Saharan Africa.

Finally, we will conduct a novel economic evaluation, using a societal perspective, to compare the relative utility of the seeking, testing, and linkage to care strategies. This analysis will take into account the economic gains to individuals and households from early diagnosis of HIV and prompt initiation of ART. We will conduct a cost-benefit analysis that focuses on the societal level economic gains that result from individuals who are successfully linked and retained in HIV care and treatment (H. Thirumurthy et al., 2013). We will comprehensively evaluate and model the costs, morbidity averted, new infections averted, and the societal impact of increased household socioeconomic status (SES) resultant from being linked to care and receiving HIV treatment. Data regarding costs will be collected using methods described above. Impacts on SES as a result of higher linkage to care and retention in care will be imputed from other studies we have conducted in Kenya and Uganda showing association between CD4 cell count and employment, income, and domestic (household) labor. We will also explore the possibility of collecting SES data from HIV-infected young women at the time they are enrolled in the linkage to care study and at 12 months. Building on previous work which included a cost effectiveness analysis of HIV prevention interventions (Alsallaq R, Buttolph J, Cleland C, Hallett T, & A., 2013; A. E. [name], [name], I., Agot,

K., Hallett, T., Cleland, C.M., Buttolph, J., Alsallaq, R, 2013) as well as economic evaluations of the effect of HIV treatment on the labor supply in Kenya (Harsha Thirumurthy, Zivin, & Goldstein, 2008), we will expand the work to include the effect of different strategies for HIV seeking, testing, and linkage, which will complete the economic evaluation for the entire HIV continua of care.

Other Analysis

Logistic regression will be used to explore predictors of timely linkage to care among girls newly diagnosed with HIV infection. Potential predictors will include behavioral (e.g, number of sex partners), demographic (e.g., age), and clinical (e.g., baseline CD4) variables assessed at baseline. Interactions between these participant characteristics and treatment conditions of the adaptive intervention also will be explored.

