The sample size for the linkage to care adaptive intervention pilot is an estimate of the number of female youth with previously undiagnosed HIV infection we anticipate reaching. The expected percentage of girls testing positive was based on our MP3 Youth pilot study (data not yet published), and we expect 9% of all tested girls to have HIV infection not previously diagnosed. Thus given a total sample size of 1,200 female youth, we anticipate enrolling about 108 previously undiagnosed HIV positive females in the adaptive intervention pilot to link HIV positive female youth to HIV treatment and care.

Sampling method: We will stratify the sample by conveniently selected sub-counties; Homa Bay municipality, Mbita sub-county and Ndhiwa sub-county. Mapping of catchment areas surrounding health facilities will be used to establish relationships with referral clinics. We select a random starting point that is within walking distance (about 5km) of the catchment area of the health facility. Approximately four hundred (400) participants will be recruited from each stratum and for each stratum it is assumed that 200 participants will be recruited through each recruitment approach. Both recruitment strategies (household and mobile event) will run concurrently until the desired sample size is reached. If needed for sample size attainment, we will expand the sampling area to a 6 - 10 km circumference of the referral clinic.

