Community Recruitment: The following areas were identified by female youths during the formative research phase of the MP3 Youth study (data not yet published) as venues where they would like to receive HIV testing services: (1) markets, (2) schools, (3) community organizations, non-governmental organizations, (4) community social events, (5) health facilities, and/or (6) churches. Therefore, these venues will serve as the sites for the community-based recruitment, where mobile health tents will be set up. Study staff will identify an appropriate location to set up

the mobile tents that will ensure that study procedures can be conducted while protecting participant confidentiality. Information on other recruitment sites and approaches will be obtained from CAB members and study recruiters hired from the same communities.

Home Based Recruitment: Households will be included if there is a female 15-24 years of age. Participants will be identified in their homes. RAs/Counselors/Study Staff will ensure that any other family members in the home understand the study is focusing on females, but the RA will be trained to make referrals for any other issues that he/she identifies within the home.

Home-based and community-based recruitment will be carried out by GIRLS study staff, who will offer participation to a potential participant by reading them the IRB-approved **recruitment script**. If a potential participant declines to participate, they will be asked to fill out a refusal survey and thanked for their time. If willing to participate, they will be given a flier and if recruited via the community-based strategy will be directed to or taken to the mobile study tent area for IC. If recruited via the home-based strategy, they will undergo IC in a private area in their household. All participants will be informed that they will be contacted in 2 weeks in order to complete an SMS survey about their HIV testing experience.

Offer of Participation

IRB approved fliers will be used to recruit participants. The fliers will be distributed and posted in areas frequented by female youth (15-24), such as (1) markets, (2) schools, (3) community organizations, non-governmental organizations, (4) community social events, (5) health facilities, and/or (6) churches.

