11.4.1 Community Based Recruitment Strategy

Possible venues for community based recruitment include: (1) markets, (2) schools, (3) community organizations, non-governmental organizations, (4) community social events, (5) near health facilities, and/or (6) churches. Therefore, these venues will serve as the sites for the community-based recruitment, where mobile health tents will be set up (see Figure 5 below), ensuring that study procedures can be conducted while protecting participant confidentiality.

Figure 5: Layout of Tents at Mobile Event

Female youth will be screened and will then flow through the series of GIRLS study tents. Some interventions will require off-site follow-up (i.e., oral HIV self-testing option or referral to standard facility based HTS).

Mobile Recruitment Layout

[figure not shown]
This section describes the anticipated layout of the mobile health community based recruitment. The events will be akin to a health campaign/health event and will have music playing and a series of tents set up where the interventions will be delivered and through which participants will flow. Below is a description of the 3 areas to be set up at the mobile event. (See Figure 6 for details).

Tent 1: Reception area where registration of interested potential female participants (15-24 years) will occur.

Tent 2: Research initiation tent where screening/eligibility, consenting, study ID allocation, and administration of CAPI behavioral questionnaire.

Tent 3: HIV testing services if participant choose to be tested by study staff (per GoK HTS Guidelines, 2015), POC CD4, DBS for VL, condom demonstration. If participant chooses to receive HTS at a health facility, a referral card will be given at this time. For those who choose the self-testing option, she will be counseled on how to use the self-test including a demonstration by staff. She will also be given a pictographic instruction sheet in English, Kiswahili or Dholuo to use as reference. Referrals for other services as needed, such as FP/contraceptives and PMTCT. SMS survey demonstration.

Figure 6: Mobile Event Layout

Participant Flow at Mobile Event

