11.4.2 Household Recruitment Strategy

On arrival to the household, study staff will introduce him or herself and enquire if there are any females between the ages of 15-24 residing in the household. The research assistant (licensed HTS counselor) will ensure that any other family members in the home understand that the study is focusing on females, but the RA will be trained to make referrals for any other issues that he/she identifies within the home.

If the female youth is not present, then RA will enquire the best time to return to the household. If female youth is present and interested in learning more about the study, RA will identify a private location in the household and explain the purpose of the study in more detail. Enrollment of participants will follow the same process of registration, consent, screening/eligibility, CAPI, HTS options, referrals etc., as participants enrolled via the community-based recruitment strategy as detailed above in Section 11.4.1.

NOTE: Individuals who do not consent/or withdraw consent, or who do not meet the study eligibility criteria will not be enrolled in the study but will receive whatever services/referral to services they require.

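### The home versus community regressions make no allowance for correlation among girls recruited at the same mobile event, and the detectable OR of 1.67 assumes independent girls

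*Combined protocol and SAP*

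**What the plan says.** Section 13.2 sets the endpoint: "The primary endpoint for comparisons of recruitment and testing strategies is newly diagnosed HIV infection". The method is in the same section: "Logistic regression analysis will be used to determine which recruitment and HIV testing approaches yield the highest proportion of newly diagnosed HIV infection". The predictors named are recruitment strategy, test type and their interaction, with youth characteristics considered as further interactions. Acceptance is handled in the same way: "rates of enrollment among eligible participants will be compared by recruitment strategy using logistic regression", and likewise for acceptance of screening.

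The two strategies recruit in different units. For community recruitment, 11.1.1 lists venues and says "these venues will serve as the sites for the community-based recruitment, where mobile health tents will be set up"; 11.4.1 adds "Possible venues for community based recruitment include: (1) markets, (2) schools, (3) community organizations" and further venue types. In home recruitment (11.4.2) staff go to a household and "enquire if there are any females between the ages of 15-24 residing in the household". On geography, 10.2 says "We select a random starting point that is within walking distance (about 5km) of the catchment area of the health facility" and "Both recruitment strategies (household and mobile event) will run concurrently until the desired sample size is reached".

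Section 15.11 gives 80% power for an OR of 1.67 with 600 girls per strategy and a 9% base rate. Sections 10.2, 13.2 and 15.11 and Table 1 contain no random effect, robust variance, ICC or design effect.

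**The concern.** A mobile event exists in one strategy only. Whatever girls at an event share (venue type, day, staff, locality, age mix) therefore adds to the error of the home versus community contrast, and ordinary logistic regression does not count it. An event fixed effect cannot be the remedy, because it would absorb the strategy effect.

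Some correlation is plausible. Section 7.2 gives HIV prevalence among females of 2.7% at ages 15-19 and 6.4% at 20-24, and venues such as schools, markets and churches may draw different ages. Acceptance of screening and enrolment could vary by event too, since girls there meet the same staff in the same setting.

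At stake are the interval for the comparison that 13.2 makes primary and the claim in 15.11 that 1,200 girls suffice to detect modest differences between recruitment strategies.

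**Working it through.** **Inputs from the protocol.** 600 girls per strategy, 9% base rate, OR 1.67 (15.11); prevalence by age (7.2). Alpha is not stated, so two-sided 5% is assumed.

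**1. Reproduce the plan's figure.** Odds at 9% are 0.09/0.91 = 0.0989. Multiplied by 1.67 they give 0.1652, a rate of 14.2%. The two-proportion formula with pooled variance and 600 independent girls per arm gives 80.05% power; solving for 80% power gives OR 1.67. The stated figure therefore has a design effect of 1.

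**2. Which ICC the documents can support.** None is given. Age supplies a partial anchor, using ICC = between-event variance / [p(1 - p)].
- Events wholly split by age, half and half: mean 4.55%, half-difference 1.85 points. ICC = 0.0185² / (0.0455 × 0.9545) = 0.008.
- The same split scaled to a 9% mean (5.3% and 12.7%): 0.016.
- Partial split (90% versus 30% aged 15-19): event rates 3.07% and 5.29%, ICC about 0.003, or about 0.006 with the same scaling factor.

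Scaling assumes that the age ratio holds for undiagnosed infection. The range used is 0.005 to 0.02, slightly above the anchor at the top to leave room for sources other than age.

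**3. Effect of event clustering.** Design effect DE = 1 + (m - 1) × ICC, applied to the community arm only; effective community n = 600/DE. For m = 20 and ICC 0.02, DE = 1 + 19 × 0.02 = 1.38 and effective n = 435. The correct standard error exceeds the naive one by a factor of √[(1 + DE)/2], here √1.19 = 1.09. Type I error of the naive test is 2 × [1 - Φ(1.96/√((1 + DE)/2))]. Ranges show which arm has the 9%.

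| Girls per event | ICC | DE | Power at OR 1.67 | Detectable OR | Type I error |
|---|---|---|---|---|---|
| 10 | 0.005 | 1.045 | 79% | 1.68 | 5.3% |
| 10 | 0.01 | 1.09 | 78% | 1.69 | 5.5% |
| 10 | 0.02 | 1.18 | 76-77% | 1.70-1.71 | 6.0% |
| 20 | 0.005 | 1.095 | 78% | 1.69 | 5.5% |
| 20 | 0.01 | 1.19 | 76-77% | 1.70-1.71 | 6.1% |
| 20 | 0.02 | 1.38 | 72-74% | 1.74-1.75 | 7.2% |

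Larger events do worse: at 40 girls and ICC 0.02, power is 65-68%, the detectable OR 1.80-1.83, and type I error about 9%.

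**4. Correlation shared with nearby homes.** If both strategies work the same area, the area component enters both arms and cancels from their difference. In null simulations with 20 girls per event and half the correlation shared, naive type I error was 5.4% and 6.3% at ICC 0.01 and 0.02, against 6.1% and 7.2% with none shared.

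**5. Which cluster to use.** With areas fully shared, clustering community girls by event and home girls by household was too conservative: type I error 3.4, 2.7 and 1.3% at ICC 0.01, 0.02 and 0.05. Clustering on the area, with the event and nearby homes together, held about 5% in every scenario simulated.

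**6. Confirmatory testing.** It mainly involves positives: 9% of 600 is 54 per strategy. With 30 events that is 1.8 per event, so even at ICC 0.05 DE is 1 + 0.8 × 0.05 = 1.04.

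**The case against.** The strongest reply is that the size is assumed. The only documentary anchor is age, and it points to the low end, where the loss is small. Recruitment is expected to be mainly of girls out of school (10.2), so a sharp age split between events is unlikely. Age is also among the characteristics that 13.2 will examine. All of this stands, and it limits the size. It does not remove the problem, because the main contrast is not stated to be age-adjusted and age is only one thing that girls at an event share.

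A second reply is that Aim 1 is called exploratory (15.11), the study is called observational (15.12), and the sample size was set by feasibility. Self-selection into venue or home is probably the larger threat, and no variance estimator addresses it. That is also true. But the comparison carries a primary endpoint and a power claim, and exploratory status does not make a too-narrow interval correct.

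Three stronger readings are tempting. A reader might infer that home recruitment is clustered by area in the same way, which would push the detectable OR towards 2.0. The documents do not establish this: the random starting point in 10.2 is not confined to home recruitment, both strategies run concurrently, and two girls in one household have a negligible effect. A reader might take an ICC of 0.05, which puts type I error above 10% at 20 girls per event; nothing in the documents supports that value. A reader might extend the point to the comparison of test types, but each girl chooses her own test (11.3), so test type is not tied to the event.

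**Conclusion.** The point holds for the home versus community contrast in the yield, screening-acceptance and enrolment models. The plan makes no provision for event clustering, and OR 1.67 assumes independent girls. If event-specific correlation is positive, the interval is too narrow and power at OR 1.67 is below 80%.

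The direction is firm under that condition; the size is not. Over the assumed range the loss runs from negligible to moderate. It would be larger with bigger events, and smaller if much of the correlation is shared with home recruitment in the same area. The figures concern yield only; the documents give no acceptance rates from which to size the screening and enrolment models. The description in 15.11 of the detectable difference as modest survives at an OR of 1.68 to 1.75, so this is a correction to make and not a reason to doubt the design.

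**What to change.** 1. On the tracking form already completed for every girl approached (11.1.1), record the mobile-event identifier for community girls, the household identifier for home girls, and the village or area for both. Without these the correction may not be recoverable later.
2. In 13.2, state that the home versus community contrast in the yield, screening and enrolment models uses cluster-robust standard errors with a small-sample correction and a t reference. Where both strategies work the same areas, the cluster is the area, holding the event and nearby homes together. Otherwise it is the event for community girls and the household for home girls. Fix the choice before outcome data are seen and, with few clusters, report the limit on inference. Confirmatory testing needs no separate provision.
3. In 15.11, say that OR 1.67 assumes independent girls, and give the detectable OR over a stated ICC and event-size range, labelled as an assumption (for example 1.68 to 1.75 for events of 10 to 20 girls and ICC 0.005 to 0.02).

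The cost is a few fields on an existing form and a few lines of text. Intervals widen somewhat: with degrees of freedom set by the number of events, the t reference alone adds about 4% with 30 events and 12% with 12, even without correlation. The stated detectable OR becomes slightly less favourable.
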